#### **1.3. Outcome measurements**

Evaluation procedures were carried out exactly the same for all the three group by an independent examiner. Another observer helped the examiner in recording hip and knee ROM during the examination. Both the examiner and observer were blinded to the study groups. The following measurements undertaken were carried out on four different occasions: baseline, after 1st session, after 3rd session, and after 6th session.

### 1.3.1. Pain intensity

Visual analog scale (VAS) was used to measure pain intensity. It consisted of a 10-cm horizontal line with 'No pain" at one end and "Worst imaginable pain" at the other end. The patient was asked to mark his current leg pain level on the line. The Minimal clinically important difference (MCID) for VAS was reported to be 1.8 - 1.9 cm (Hägg et al., 2003). VAS is a valid and reliable measurement of pain intensity (Ferreira-Valente et al., 2011).

### 1.3.2. Hip ROM with SLR

The patient was in supine position with their head in neutral and flat on the bed without pillows. The examiner supported the knee in full extension using his proximal hand, whereas distal hand was used to maintain the ankle position in a neutral position. The examiner passively raised the examined leg until the patient reported reproduction of his symptoms, or until the examiner felt significant resistance to SLR (Martin et al., 2014; Walsh and Hall, 2009a).

The independent examiner performed the SLR test for asymptomatic then symptomatic limb. A bubble inclinometer (Fabrication Enterprise Inc., White Plains, New York 10602, and U.S.A) was secured just proximal to the ankle joint using double adhesive tape. The inclinometer was directed towards the medial aspect of the leg so that the examiner could not see it. The observer adjusted the fluid to zero level before testing. The observer recorded the ROM when the patient started feeling reproduction of his symptoms or the examiner felt significant resistance (Figure 1).

## 3.3.3 Knee flexion ROM with the Slump test

In the slump test, the patient seated at the edge of the bed with legs dangling freely and knee at an angle of 90° flexion. The patient's trunk was placed in slumped position with cervical flexion and hands were together behind the back. The distal hand of the examiner was used to maintain the ankle in neutral position. The examiner proximal hand was used to maintain the slump position of the patient trunk. The examiner instructs the patient verbally to maintain his head in flexed position. The examiner used his distal hand to passively extend the examined knee until the patient felt his symptoms, or until the examiner felt significant resistance (Walsh and Hall, 2009a). The measurement of knee flexion ROM in a slump was taken for the asymptomatic then symptomatic limb.

A bubble inclinometer was secured just proximal to the ankle joint using double adhesive tape. The inclinometer was directed towards the medial aspect of the leg so that the examiner could not see it. The observer adjusted the fluid to zero level before testing and recorded the angle during the test. The observer recorded the measurement of the inclinometer at the point of symptoms reproduction or the feeling of resistance (Walsh and Hall, 2009b) (Figure 2).

*Figure 1: Straight leg raising test. showing the placement of inclinometer to measure hip range of motion from starting position (A) to end position (B).* 

Figure 2: End position of the slump test. during which the observer was recording knee range of motion and the examiner performed the test.

## **1.4. Interventions**

Each patient received therapeutic sessions over 2 weeks (3 sessions/ week). All patients in all groups received Transcutaneous Electric Nerve Stimulation (TENS). In addition, T-group received tensioner neural mobilization technique and S-group received slider neural mobilization technique.

## 1.4.1. TENS (All study groups)

TENS device (Sonicplus 692V, ENRAF-NONIUS, Rotterdam) was applied at a pulse frequency of 100 Hz (Thiese et al., 2013). A single channel, two surface electrodes, were used for stimulation over a session period of 15 minutes (Itoh et al., 2009). The device electrodes were placed on the painful paraspinal areas of the back. The intensity was set to enable a clear tingling sensation above the sensory threshold of the patient (Barker et al., 2008; Itoh et al., 2009) (Figure 3).

Figure 3 : Transcutaneous electrical nerve stimulation (TENS).

## 1.4.2. T-Group (Tensioner technique)

This technique was done in a sitting slump position. The patient sat on the edge of the bed with the neck and trunk in neutral, hips and knees in 90° flexion and ankles in resting plantar flexion. The back of the patient's knees touched the bed edge. The patient was asked to move the neck and trunk into flexion slouched position, the treated knee in extension, and ankle in dorsiflexed simultaneously (Phase 1). Then the patient extended the neck and trunk, flexed the knee, and plantarflexed the ankle simultaneously (Phase 2). Tensioner technique was performed for 10

repetitions over 2 sets. The patient was given a 2-minutes resting time between the sets (Herrington, 2006; Shacklock, 2005) (Figure 4).

[figure not shown]

Figure 4 : The tensioner technique: A) starting position, B) phase 1, and C) phase 2.

### S - Group (Slider technique)

This technique was also done in a sitting slump position. The patient sat on the edge of the bed, with the neck and trunk in flexion, hips, and knees in 90° flexion and ankles in resting plantar flexion. The back of patient's knees touched the bed edge. The patient was asked to move the neck into extension, the treated knee in extension, and ankle in dorsiflexion simultaneously (Phase 1). Then the patient flexed the neck and trunk, flexed the treated knee and plantarflexed the ankle Simultaneously (Phase 2). Slider technique was carried out for 10 repetitions over 2 sets. The patient was given a 2-minutes resting time between the sets (Herrington, 2006; Shacklock, 2005) (Figure 5).

Figure 5 : The slider technique: A) starting position, B) phase 1, and C) phase 2.

### **1.5. Statistical analysis**

SPSS software (version 23, IBM Corporation, New York) was used for statistical analysis. Descriptive data of mean and standard deviation was obtained for all data. The baseline between groups' comparisons on clinical and demographic variables (BMI, age, and VAS) was performed using one-way analysis of variance (ANOVA). A two-way mixed design ANOVA (MANOVA) with post-hoc (Bonferonni Correction) was used to calculate the differences in outcomes measurements with TIME (baseline, 1st, 3rd, and 6th session) as a within-groups factor and GROUP (control, slider, and tensioner) as a between-group factor. The effect size was also calculated with Cohen's *d* to estimate the magnitude of differences within and between groups [small (d = 0.2), medium (d = 0.5), and large (d = 0.8)]. Pearson's correlation was performed to assess the relationship between pains, hip flexion ROM in SLR, knee flexion ROM in slump. The significant level was set at P < 0. 05.

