### **1.2.** Participants

The sample size was calculated using G\*power software Version 3.0.10. Data from Tambekar et al. (2016) was used (effect size 0.82,  $\alpha = 0.05$ , power= 0.95). The calculation resulted in a total of 51 participants. Lumbosacral radiculopathy patients with dominant peripheral sensitization of unilateral leg pain were recruited. The patient was diagnosed with peripheral sensitization if they fulfilled the criteria suggested by Schäfer et al. (2009) which included: S-LANSS score < 12, negative sensory and motor examination, and positive neural tissue provocation tests (straight leg raising test, slump test). The inclusion criteria were: adult, pain duration of more than 3 months, patients were diagnosed with peripheral sensitization. Patients with one or more of following criteria were excluded from this study: S-LANSS score  $\geq 12$ , motor or sensory deficits, history of back or lower extremity surgeries, bilateral referred pain, patients with TENS contraindications as described in Jones and Johnson (2009) such as pacemakers and cardiovascular problems, epilepsy, active malignancy, dermatological conditions, and diminished pain sensation.

At SFH, KFHU and DMC outpatients' clinics, the physician referred patients diagnosed with lumbar radiculopathy or lumbosacral radiculopathy with negative dermatomes, myotomes and reflexes examinations finding to the primary investigator. In the initial appointment, the primary investigator explained to each participant the aims and the general procedures of the study. If agreed to participate, the patient signed the consent form (Appendix B, C). The independent examiner started the examination for eligibility with S-LANSS assessment (Appendix D) and an examination of SLR and slump tests. If eligible, the patient was assigned alternatively to one of the three study groups: tensioner group (T- group), slider group (S- group), or control group (C- group). Patients were blinded to the intervention details until they were assigned to one of the study groups. In the alteration type of allocation of groups allocation, the first patient was assigned to slider group, the second was assigned to the tensioner and the third to control group. This order continued even if there was any withdraw until we reached the end of the list then we started filling the gaps in the list from the top with new participants.

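### Baseline enters the mixed ANOVA only as a TIME level and never as a covariate, which costs precision and clarity; type I error holds only under conditions the plan does not secure

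*Combined protocol and SAP*

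**What the plan says.** Section 1.3 has every outcome measured at baseline and after sessions 1, 3 and 6: "The following measurements undertaken were carried out on four different occasions". Section 1.5 analyses them thus: "A two-way mixed design ANOVA (MANOVA) with post-hoc (Bonferonni Correction) was used to calculate the differences in outcomes measurements". Baseline is the first of the four levels of TIME, which enters "as a within-groups factor and GROUP (control, slider, and tensioner) as a between-group factor". No covariate is named anywhere.

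The only other planned use of baseline is a set of between-group "comparisons on clinical and demographic variables (BMI, age, and VAS) was performed using one-way analysis of variance (ANOVA". Hip ROM and knee ROM, two of the three outcomes, are not in that list, and no adjustment follows from the test. Cohen's d is planned "to estimate the magnitude of differences within and between groups", with no word on baseline. The plan does not say which post-hoc contrasts are made, which effect answers the trial's question, or which time point is primary.

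On size and allocation, section 1.2 gives "effect size 0.82" and says "The calculation resulted in a total of 51 participants". It also says: "If eligible, the patient was assigned alternatively to one of the three study groups". The order is fixed, and gaps left by withdrawals are filled later with new participants.

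**The concern.** Each patient's own starting value is collected, yet no planned group difference is stated to be adjusted for it. Three consequences follow.

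- The GROUP main effect mixes a pre-treatment level into the treatment comparison.
- The GROUP x TIME test can show that time courses differ, but does not say by how much any two groups differ.
- A reader of the pairwise results and Cohen's d could not tell whether baseline differences had been removed.

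If the post-hoc tests compare raw means at a visit, which is one possible reading, a fraction of any baseline imbalance equal to the baseline-to-follow-up correlation carries into the contrast. With small groups, that imbalance can be sizeable by chance alone. With alternation it need not be only chance.

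**Working it through.** **Inputs from the documents.** Total 51, three groups, alpha 0.05, four occasions, effect size 0.82. Alternation implies equal groups: 51/3 = 17.

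**Assumed, not in the documents.** 0.82 is a pairwise d; tests are two-sided; alpha is 0.05/3 for three pairwise contrasts; SD is the same at each visit; baseline-to-follow-up correlation r = 0.3 / 0.5 / 0.7.

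**The plan's own figure.** 51 does not follow from the stated inputs alone. At power 0.95, a one-way ANOVA needs 27 (f = 0.82) or 96 (f = 0.41), and a two-sided two-sample t-test with d = 0.82 needs 40 per arm. A repeated-measures ANOVA with f = 0.41, two time points and zero correlation gives 51, but the plan states none of those inputs. This is a separate matter; 51 is used here only to fix n.

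**Dilution.** A sustained effect D has group differences 0, D, D, D over the four levels. Their mean is 3D/4.

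**Interaction df.** (3 - 1)(4 - 1) = 6.

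**Chance imbalance.** The SD of a two-group baseline difference is sqrt(2/17) = 0.343 SD. At r = 0.5, a raw follow-up contrast carries 0.5 x 0.343 = 0.17 SD of it.

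**Pairwise power at a visit where the effect is 0.82 SD.** Noncentrality = 0.82 / sqrt(2v/17); the critical t is 2.48 on 48 df (raw, change) or 47 df (adjusted).

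| Contrast | v | Noncentrality, r = 0.3 / 0.5 / 0.7 | Power |
|---|---|---|---|
| Raw means | 1 | 2.39 | 47% |
| Change | 2(1 - r) = 1.4 / 1.0 / 0.6 | 2.02 / 2.39 / 3.09 | 33 / 47 / 73% |
| Baseline-adjusted | 1 - r^2 = 0.91 / 0.75 / 0.51 | 2.51 / 2.76 / 3.35 | 51 / 61 / 80% |

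Adjusted CI width is sqrt(1 - r^2) = 0.95 / 0.87 / 0.71 of raw; estimating the slope costs about 1% of that.

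**Where the gain shrinks.** If correlation decays as AR(1) with lag-1 value r, the baseline-to-session-6 correlation is r^3 = 0.03 / 0.13 / 0.34. Session-6 width is then 1.01 / 1.00 / 0.95 of raw, slope cost included, and 0.99 / 0.94 / 0.82 for the post-treatment average. If 0.82 is Cohen's f with both active arms shifted equally, d = 0.82 x 3/sqrt(2) = 1.74; power is 99% or more raw or adjusted, and only precision improves. With evenly spaced groups, adjacent d = 0.82 x sqrt(6)/2 = 1.00, and power is 67% raw against 72 / 81 / 94% adjusted.

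**Omnibus power.** Simulated at 0.05 with 20,000 trials per cell, both active arms shifted by 0.82 SD. CS is compound symmetry; the interaction is Greenhouse-Geisser corrected; the early effect is 1, 1/2, 0 of 0.82 at sessions 1, 3, 6. Entries are % at r = 0.3 / 0.5 / 0.7.

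| Pattern | GROUP main effect | GROUP x TIME | Session-6 ANCOVA | Adjusted average |
|---|---|---|---|---|
| Sustained, CS | 75/63/52 | 50/68/91 | 70/79/93 | 95/97/99 |
| Sustained, AR(1) | 83/71/58 | 43/50/67 | 66/66/71 | 95/92/93 |
| Gone by session 6, CS | 24/19/16 | 46/63/87 | 5/5/5 | 41/43/56 |
| Gone by session 6, AR(1) | 28/22/18 | 39/47/67 | 5/5/5 | 39/35/37 |

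For the early effect, a joint adjusted test over the three post-baseline visits (6 df) gives 56/68/88 (CS) and 52/60/84 (AR(1)).

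**Type I error, exchangeable groups.** At r = 0.3 to 0.7 the main effect rejects 5.0-5.1%, the corrected interaction 4.4-4.9% and ANCOVA 4.9-5.3%. The uncorrected interaction under AR(1) rejects 5.2 / 5.9 / 6.6%.

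**Type I error, systematic gap.** One group is shifted at baseline by an assumed 0.25 / 0.5 / 1.0 SD that acts only through measured baseline (CS, r = 0.5, no treatment effect). Rejection is 8 / 20 / 63% for the main effect, 6 / 9 / 27% for the uncorrected interaction, 7 / 12 / 30% for the change contrast and about 5% throughout for ANCOVA. If the gap instead persisted unchanged, change would remove it and ANCOVA would leave (1 - r) of it.

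**The case against.** A TIME x GROUP mixed ANOVA is a recognised repeated-measures analysis, and its interaction compares changes from baseline between groups. So a reader who infers that the plan ignores baseline goes too far: the contrasts and Cohen's d are under-specified, not shown to be raw. That stands, and the point is limited accordingly.

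The size of the gain also depends on a correlation, a covariance structure and a meaning of 0.82 that the documents do not give. Against change scores at r = 0.7 the gain is modest (73% to 80%). This stands too.

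A reader might infer that adjustment beats the planned analysis throughout. It does not. The adjusted average beat the GROUP main effect in every cell simulated at r = 0.3 to 0.7, but the plan does not make that effect its test of interest. For an effect gone by session 6, the adjusted average loses to the planned interaction in five of six cells and ties in the other, and session-6 ANCOVA has no power. Only the joint test keeps what the interaction finds, and it too can lose (81% v 90% under AR(1), r = 0.9, growing effect).

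The MANOVA label may denote the multivariate test, which needs no sphericity. Its power differs from the corrected univariate test in both directions: 35% v 52% for a growing effect and 85% v 67% for an early one, both AR(1) with r = 0.7.

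What survives is that no group estimate in the plan is stated to use the patient's own baseline, although every patient has one.

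**Conclusion.** The point holds as a recommended change, not a fatal flaw. The textual part is certain: baseline is a TIME level, no covariate is named, and no group contrast is stated to be adjusted. The 3/4 dilution of the main effect for a sustained effect is arithmetic. At a single visit, adjustment takes pairwise power from 47% to 51 / 61 / 80% under the stated assumptions, with little or no gain at session 6 if correlation decays as AR(1).

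Two opposite inferences about false positives are tempting, and neither is supported. One is that type I error is safe regardless. It is safe only with groups exchangeable at baseline and with sphericity handled, or the multivariate test used; alternation with gap-filling does not assure the first, and the plan states no sphericity correction. The other is that type I error is in fact inflated. The documents do not show that any systematic baseline gap occurred, and the simulated excess rests on an assumed gap.

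**What to change.** For each outcome, model the three post-baseline assessments with GROUP, TIME, GROUP x TIME, the patient's own baseline value of that outcome and baseline x TIME, with unstructured covariance. Then:

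- Report Bonferroni-adjusted pairwise group contrasts with 95% CIs at session 6 and averaged over the post-treatment visits, and name one of the two as primary.
- Base the between-group Cohen's d on the adjusted contrast and state which SD divides it.
- Keep the GROUP x TIME test, and add the joint test of GROUP and GROUP x TIME so that an effect present only early is not missed.
- State that adjustment removes only measured baseline imbalance and does not cure non-random allocation. If groups differ systematically at baseline, adjusted and change-score contrasts answer different questions.

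The cost is one paragraph of section 1.5, three baseline parameters per outcome, and one residual df per visit contrast (48 to 47). No new data are needed. Section 1.5 is written in the past tense; if results are already known, label the model as amended and report it beside the planned ANOVA, not in its place.

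### Section 1.5 leaves open which GROUP × TIME test is used and how non-sphericity is handled, and its model treats baseline as an outcome occasion

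*Combined protocol and SAP*

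**What the plan says.** Section 1.5 gives the main analysis as follows: "A two-way mixed design ANOVA (MANOVA) with post-hoc (Bonferonni Correction) was used to calculate the differences in outcomes measurements with TIME". The factors are "TIME (baseline, 1 st , 3 rd , and 6 th session) as a within-groups factor" and "GROUP (control, slider, and tensioner) as a between-group factor", and the threshold is given by "The significant level was set at P < 0. 05".

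Section 1.3 says the outcomes (leg pain, hip range in the straight leg raise, knee range in the slump test) were "carried out on four different occasions: baseline, after 1 st session, after 3 rd session, and after 6 th session". Section 1.4 places all sessions within two weeks: "Each patient received therapeutic sessions over 2 weeks (3 sessions/ week").

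Section 1.5 names no sphericity check, no degrees-of-freedom correction and no multivariate statistic, and it does not explain the bracketed MANOVA. The Bonferroni correction is attached to the post-hoc comparisons, so it does not alter the omnibus F test. Baseline enters only as the first level of TIME. No correlation or covariance of the repeated measures is given anywhere.

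**The concern.** In a mixed ANOVA, GROUP × TIME asks whether the arms change differently. The plan does not name it as decisive, but it is the term closest to the trial's question. The univariate F test for that term, and for TIME, is exact only under sphericity, meaning that all pairwise differences between occasions have equal variance. With one pre-treatment and three on-treatment occasions, after 0, 1, 3 and 6 sessions, neighbouring measurements may well correlate more strongly than distant ones, and then sphericity fails.

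Two things are at stake for each of the three outcomes:

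- **Error rate.** An uncorrected test would reject too often. A choice between univariate and multivariate p-values made after the data are seen would do so as well.
- **Efficiency.** The group comparison of interest is the difference after treatment, given where patients started. Making baseline a level of TIME turns it into a comparison of changes, or, in the GROUP main effect, averages in an occasion on which no treatment has yet been given.

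**Working it through.** **Inputs from the documents.** Three groups, four occasions, 51 patients in total (section 1.2), level 0.05. Equal groups give 17 per arm. The degrees of freedom for GROUP × TIME are (3 − 1)(4 − 1) = 6 and (51 − 3)(4 − 1) = 144.

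**Input not in the documents.** The covariance Σ of the four measurements. What matters is epsilon = tr(A)² / (3 tr(A²)), with A = C′ΣC and C a set of three orthonormal contrasts. Epsilon is 1 under sphericity and cannot fall below 1/3. It is assumed below and a range is shown.

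**Step 1: the plan's 5%.** At epsilon 1 the test refers to F(6, 144), whose 95% point is 2.162, so the size is 5.0%. Simulation gives 5.1%. The stated level is reproduced for this case.

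**Step 2: Box approximation for the uncorrected test.** Size ≈ P[F(6ε, 144ε) > 2.162].

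| Epsilon | Degrees of freedom | Size |
|---|---|---|
| 1.0 | 6, 144 | 5.00% |
| 0.9 | 5.4, 129.6 | 5.73% |
| 0.8 | 4.8, 115.2 | 6.57% |
| 0.7 | 4.2, 100.8 | 7.55% |
| 0.6 | 3.6, 86.4 | 8.68% |
| 1/3 (lower bound) | 2, 48 | 12.62% |

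**Step 3: simulation under no effect.** 3 × 17 patients. There were 100,000 trials per pattern for the single tests and 40,000 for the last column. Serial correlation is r per session on the 0, 1, 3, 6 scale.

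| Assumed pattern | Epsilon | Uncorrected | Greenhouse-Geisser | Multivariate (Wilks) | Uncorrected or Wilks |
|---|---|---|---|---|---|
| Equal correlation 0.5 | 1.00 | 5.1% | 4.6% | 5.0% | 6.3% |
| r = 0.5 | 0.90 | 5.8% | 4.9% | 5.2% | 7.4% |
| r = 0.8 | 0.73 | 7.1% | 5.0% | 5.0% | 8.9% |
| r = 0.9 | 0.67 | 7.8% | 5.1% | 5.2% | 9.9% |

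Across all runs the uncorrected size for r = 0.5–0.9 lay between 5.4% and 8.4%. The 100,000-trial figures of 5.8–7.8% are the most precise, and the Box values agree with them. Serial correlation is not required: with post-treatment occasions correlated 0.8 with each other and 0.5 with baseline, at equal variances, epsilon is 0.73 and the size about 7.1%. Choosing between Greenhouse-Geisser and Wilks after seeing the data still gives 6.1–7.8%.

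**Step 4: adjusting for baseline.** Let r be the correlation between baseline and session 6, with equal variances σ². A change score has residual variance 2(1 − r)σ²; adjustment for baseline leaves (1 − r²)σ². The ratio is (1 + r)/2.

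- At r = 0.5: 0.75/1.00 = 0.75.
- At 0.8 per session, r = 0.8⁶ = 0.262, and the ratio is 0.931/1.476 = 0.63.

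Both values of r are assumptions, but the ratio is below 1 whenever r is below 1. In simulation the baseline-adjusted comparison at session 6 held 4.9–5.7%, and no sphericity assumption enters it.

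**The case against.** A reader might infer that the trial's GROUP × TIME test does run at 6.6–8.2%. The documents do not support that. Such a range corresponds to epsilon between about 0.80 and 0.64, and no covariance is reported. Under sphericity the uncorrected test is exact, and with r = 0.5 per session the excess is under one percentage point. Unequal spacing and a pre/post distinction do not by themselves break sphericity.

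A reader might also infer that no correction was applied. The plan is silent, which is a different thing. The bracketed MANOVA may mean the multivariate within-subject test, which needs no sphericity and held about 5% in every pattern tried. Nor does the plan say that whichever p-value is smaller will be reported, so the 6–10% figure describes what the open wording permits and not what was done.

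All of this stands, and it limits the size that can be claimed. It does not close the gap: the wording names a univariate and a multivariate analysis together and commits to neither. It also leaves the treatment of baseline untouched.

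On the remedy, it is fair to say that the full mixed model was not simulated, only the session-6 baseline-adjusted comparison. With about 17 patients per arm the mixed model's error rate depends on the degrees-of-freedom method, so that method must be named.

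**Conclusion.** The point holds in conditional form. Section 1.5 does not fix the test or the handling of non-sphericity. If the univariate GROUP × TIME test is run uncorrected, its size is 5% under sphericity and about 5.4–8.4% under assumed serial correlation of 0.5–0.9 per session. The theoretical ceiling is near 12.6%, at the lower bound of epsilon. A multivariate test fixed beforehand holds 5%; a free choice afterwards gives about 6–10%. These figures assume 17 complete patients per arm, normal data and a common covariance in the three groups.

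The inflation is moderate and may be nil, so on this ground alone the request would be for one missing sentence. What makes a change of method worthwhile is that the data already collected support a baseline-adjusted analysis that needs no sphericity and compares the arms more precisely.

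**What to change.** **Preferred.** For each outcome, replace the ANOVA in section 1.5 with a mixed model on the three post-baseline occasions. Its terms are group, occasion, group × occasion and the baseline value, with unstructured covariance and Kenward-Roger or Satterthwaite degrees of freedom. If the installed SPSS version offers neither, use a baseline-adjusted ANCOVA at session 6. Base the conclusion on the three between-group contrasts at session 6, Bonferroni-adjusted (0.05/3 = 0.0167 each).

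**If the ANOVA is kept.** Name one test in advance. Either report Greenhouse-Geisser-corrected TIME and GROUP × TIME for every outcome, whatever Mauchly's test shows, and remove the bracketed MANOVA; or state that the multivariate test alone is used.

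**Cost.** A few sentences in section 1.5 and no new data. Keeping the ANOVA with the correction gives slightly larger p-values for TIME and GROUP × TIME. With the mixed model, the conclusion rests on one named occasion. Section 1.5 is written in the past tense; if the analysis has already been run, the change is a reanalysis of the same data and should be reported as such.

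### Bonferroni on the three group pairs is valid but gives up power: for one outcome at one fixed visit, Holm's step-down or the closed three-group test holds 5% with more

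*Combined protocol and SAP*

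**What the plan says.** Section 1.5 plans a mixed ANOVA in which time has four levels and the other factor is "GROUP (control, slider, and tensioner) as a between-group factor". Comparisons after the ANOVA are described by "post-hoc (Bonferonni Correction) was used to calculate the differences in outcomes measurements", and the threshold by "The significant level was set at P < 0. 05". The text does not say which comparisons share the Bonferroni correction: the three group pairs, the six time pairs, or the group pairs at each time.

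Section 1.2 gives the size: "The calculation resulted in a total of 51 participants", based on "effect size 0.82", two-group or multi-group metric not stated, with alpha 0.05 and power 0.95. On allocation it says that "the patient was assigned alternatively to one of the three study groups", and vacated places are refilled, so a full list gives 17 per arm. Section 1.3 has the measurements "carried out on four different occasions: baseline" and after the 1st, 3rd and 6th sessions. No outcome or visit is named as primary.

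**The concern.** The three pairwise contrasts (each technique against TENS alone, and slider against tensioner) are what a reader will want from this trial. With 17 per arm, power for them is scarce.

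Three groups are a special case. If all three means are equal, a 2-df F-test at 5% already limits the chance of any false claim to 5%. If exactly two are equal, only one pair is truly null, and testing it at 5% is enough. An F-test at 5% followed by each pair at 5% is therefore a closed test with strong familywise control. Holm's step-down needs no preceding F-test and rejects everything that Bonferroni rejects. Testing every pair at 0.0167 thus makes a missed true difference more likely than the 5% familywise level requires.

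**Working it through.** **Inputs.** Total 51 over three arms in turn (section 1.2): 51/3 = 17 per arm, error df = 51 − 3 = 48. Alpha is 0.05 (section 1.5). Assumptions, because the plan is silent: two-sided tests, Bonferroni family = three group pairs at one visit, and 0.82 = difference in means divided by the SD.

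**The plan's own figure.** The stated 51 does not settle what 0.82 means. At 95% power, a two-sided two-sample t-test with d = 0.82 needs 40 per arm. A one-way ANOVA on three groups needs 27 in total if f = 0.82, or 96 if f = 0.41. A repeated-measures F-test returns 51 only under settings that the plan does not state, for example f = 0.41, two measurements and zero correlation. The standardized-difference reading therefore stays an assumption, and other effects are shown below.

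**Bonferroni power, one pair.** Noncentrality = 0.82 × √(17/2) = 2.39. The critical value is t(48) at 1 − 0.05/6, which is 2.48. The noncentral t distribution then gives power of 47.0%.

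**Three procedures compared.** Simulation, 400,000 runs, 17 per arm, pooled error with 48 df, one arm 0.82 SD from two equal arms:

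| | Bonferroni | Holm | Closed test |
|---|---|---|---|
| Power per true pair | 47.0% | 50.1% | 57.7% |
| Power for both true pairs | 31.0% | 37.1% | 49.0% |

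The closed test gains 57.7 − 47.0 = 10.7 points per pair and 49.0 − 31.0 = 18.0 for both. Holm gains 50.1 − 47.0 = 3.1 and 37.1 − 31.0 = 6.1.

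**Familywise error, one outcome at one visit.** With all means equal it is 4.3% for Bonferroni and Holm, and 4.97% for the closed test. With two means equal, the closed test stays at about 5.0% or below.

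**Other patterns.** Closed test minus Bonferroni, three arm means in SD units:

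- 0/0.41/0.82: +4.7 points for the largest pair, +8.7 for each adjacent pair.
- 0/0.5/0.5: +5.4 per pair, +8.2 for both.
- 0/1.2/1.2: +7.1 per pair, +12.7 for both.

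Holm gains about 1 to 5 points over these patterns.

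**Interval width.** Half-width = t × √(2/17) = t × 0.343. With Bonferroni this is 2.48 × 0.343 = 0.85 SD, with simultaneous coverage. Unadjusted it is 2.01 × 0.343 = 0.69 SD, without it.

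**Why not the time pairs or the interaction test.** Four times give six pairs. If one time differs strongly and three are equal, an overall F-test is almost always significant and three null pairs are then tested unadjusted, with familywise error of about 12% (independent-sample figure for three equal means). The group-by-time test, with (3 − 1) × (4 − 1) = 6 df, fails as the first step for a similar reason: differences at other visits can make it significant while all three arms are equal at the visit tested.

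**The case against.** The strongest objection is that nothing here is wrong with the plan. Bonferroni after ANOVA controls the error for the pairs and gives intervals that agree with the tests. This stands: the point is about efficiency only.

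A reader might go further and infer that any step-down or closed test recovers 11 to 18 points of power at no cost. The documents do not support that:

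- The range belongs to the closed test alone, under one effect pattern and one reading of 0.82. Holm gains 3 to 6 points in the same case.
- There is a cost. Matching simultaneous intervals are lost. In the 0/0.82/0.82 case, the chance of a false claim between the two equal arms rises from 1.7% (0.05/3) to 4.8%. That is within 5%, but more of the allowance is spent.
- The chance of declaring at least one pair different rises only from 63.2% to 66.5%.

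A second objection is that 5% holds only within one outcome and visit. This also stands. Under assumed correlations of 0 to 0.5 between outcomes and 0.5 to 0.7 between visits, three outcomes at one visit give a familywise error of 11.2–12.2% with Bonferroni over three pairs and 12.8–14.0% with the closed test. Three outcomes at three post-baseline visits give 24.0–30.0% and 26.6–33.6%. Bonferroni over three pairs does not close that gap, and the closed test widens it slightly.

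Finally, section 1.5 is written in the past tense. The documents do not show whether results were known, so a switch to a more liberal test could be post hoc.

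**Conclusion.** The point holds as an inexpensive improvement, not as an error. For the three group pairs, on one outcome at one visit fixed in advance, Holm and the closed test both keep 5% familywise control and have more power than Bonferroni. In the 0.82 case with two equal arms, Holm adds 3 points per pair and 6 for both pairs; the closed test adds 11 and 18. In the other patterns tried, the gains are about 1 to 5 and 5 to 13 points.

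This rests on 17 evaluable patients per arm, two-sided tests, equal variances, 0.82 read as a standardized difference, and a Bonferroni family of three group pairs. The plan states neither of the last two.

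It would also be wrong to infer that the change rescues the trial's power. Even in the 0.82 case the closed test reaches 58% per pair, against the 95% used in the sample-size calculation. Nor does it supply the missing primary outcome and visit.

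**What to change.** In section 1.5, separate the group comparisons from the time comparisons, for example:

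*For each outcome, the three groups are compared at one visit only, after the 6th session. The three pairwise P values are tested by Holm's step-down at a familywise level of 5%. Comparisons among the six pairs of times keep the Bonferroni correction.*

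The 6th session is an example; whichever visit is chosen must be stated as the only one. To obtain the larger gain, replace the Holm sentence by:

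*The 2-df group test at this visit is done at 5%; if it is significant, each of the three pairwise differences is tested at 5%.*

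The first step must be that 2-df test, not the 6-df group-by-time test.

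The cost is a few lines of text and the choice of a visit, which the plan lacks. Both procedures work from unadjusted pairwise P values. Report ordinary 95% intervals beside the tests, and say that they lack simultaneous coverage and that the 5% applies within one outcome and visit, not across the three outcomes and three post-baseline visits. If outcome data have already been seen, keep Bonferroni as the planned analysis and give the new one as a labelled sensitivity analysis.
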